Evaluation of pharmacist interventions in lipid management for secondary prevention

NCT06647238

Document date: October 24, 2024

Lipids Research Protocol

Title: Second Time's the Charm: Evaluation of pharmacist interventions in lipid management for secondary prevention

Principal Investigator: [name], BCACP, CDCES, CPP

Co-Investigators:

[name], MSCR

[name], CDCES, BCPS, CPP, DPLA

[name], CDCES, BCPS, CPP

[name], PharmD

[name], BCACP, CDCES, CPP

[name], BCPS, CPP, CDCES

Background/Significance:

Studies have shown prevention of cardiovascular adverse events is directly proportional to percent reduction in LDL.¹ This evidence explains why LDL targets for secondary prevention have continued to be lowered. Cholesterol guidelines have been updated recently and encourage the use of multiple lipid lowering therapies, in addition to statins, for secondary prevention. However, these novel agents can be expensive and difficult to acquire, making prescribing challenging for providers.

This project aims to utilize a pharmacist to evaluate patients for evidence-based therapy and initiate guideline-directed lipid lowering therapy as indicated.

Study Purpose:

The primary objective of this research project is to compare the effect of pharmacist interventions versus usual care in the implementation of guideline directed lipid lowering therapies for secondary prevention.

Study Design: prospective interventional study

Methods/Data Collection

Patient Identification:

- Internal medicine providers and PharmDs will identify patients who are not meeting LDL goals for secondary prevention and could benefit from pharmacist intervention
- SlicerDicer will be utilized to select patients for the control arm as well as potentially for the intervention arm if referrals alone do not meet the sample size goal

Collected data will be stored on a secure Atrium server and de-identified. Data will be analyzed utilizing REDCap. Data collected via EPIC may include:

- Demographic information (age, gender, race)
- Baseline information (recent lipid panel, Lp(a) history)
- Initial hyperlipidemia treatment
- Relevant lab information (renal function, electrolyte values)
- Other co-morbidities (diabetes, CKD, etc)
- Insurance type
- Follow up appointments
- Other relevant patient information for an appropriate hyperlipidemia treatment recommendation

The study period is expected to be 5 months (anticipated November 2024-March 2025).

Inclusion Criteria:

- Age \geq 18 yo
- Diagnosis of coronary artery disease
- Most recent LDL value > 55
- PCP at 1 of 6 identified clinics

Exclusion Criteria:

- Patients who are no longer an active patient of one of the internal medicine practices
- Patients whose cholesterol is managed by another practice
- Women of childbearing age/potential
- Patients residing in hospice/LTC facilities
- End-stage liver disease

Practice Sites:

- Kannapolis Internal Medicine
- Concord Internal Medicine
- Ardsley Internal Medicine – Harrisburg

- Atrium Health Primary Care Cabarrus Family Medicine – Locust
- Atrium Health Primary Care Cabarrus Family Medicine - Midland

In-person, initial visit:

- Perform medication reconciliation and adherence assessment
- Assess recent laps in EPIC profile
- Educate patient on background of project (pharmacist lipid intervention), provide information sheet, future steps/plans
- Adjust hyperlipidemia treatment, which is part of the routine clinical practice under the collaborative practice agreement.
 - CPP is a licensure that is obtained from the NC Board of Pharmacy and is renewed yearly; CPPs must complete an additional 20 hours of continuing education each year
 - A CPP has an established collaborative practice agreement (CPA) with a supervising physician that outlines the role of the CPP
 - Each pharmacist working on this project either practice as a CPP or are under the direct supervision of CPP
- Order appropriate lab work
- Arrange follow-up with patient regarding medication changes (phone visit)
 - Follow up visits will be scheduled every 6-8 weeks as needed based on patient-specific needs
 - Once LDL<55 (controlled), no further follow up will be scheduled with PharmD
- Will also plan to check Lp(a) for patients who have never had this lab assessed
 - Will provide information sheet on this lab and what to do if it comes back as elevated

Follow up visits:

- Repeat lipid panel prior to appointment, review results
- Assess adherence and access to recommended therapy
- Discuss therapy adjustments
- Set up next follow up visits

The initial in-person visit, or a follow-up telephonic phone visit may be completed by another embedded pharmacist within one of the clinics included in study due to schedule availability. Members of the PharmD team will be trained and follow the protocol during their visits.

Medications are being adjusted as per the usual care services provided by their PCP office and

PharmD services that are already in place at each practice. Adjustments to medication regimens, comorbidities, and concurrent medications will be made based on national guidelines and evidence-based recommendations that are already allowable by CPP and per our collaborative practice agreement. Any costs/risk associated with medication changes is no additional risk than if they do not participate in the study and would still be subject to these medication changes if they weren't participating in the study. This study and applicable additional intervention are simply offering additional care services provided by a PharmD for closer follow up and offering patients assistance with access to newer therapeutic options.

Control Group:

Patients meeting inclusion criteria will be pulled from SlicerDicer. Any patients previously referred to the project by their provider will be excluded from the control group. Patients included in the report will then be randomized and chosen for retrospective chart review. The goal will be to include 75 patients in both the intervention and control arms. Investigators will perform retrospective chart review for the study period and record the same data as collected for patients in the intervention arm.

Primary endpoint: patients with LDL within goal (<55) (yes/no)

Secondary endpoints:

- Percent LDL reduction (will use baseline LDL and lowest LDL)
- Medication related problems identified and solved
- Medications initiated or titrated
- Number of patients who were provided assistance with access to medication
- Prevalence of elevated Lp(a)

Data and Safety Monitoring:

Principal investigator and co-investigators will meet monthly to re-evaluate patient enrollment and ensure all investigators are adhering to study protocol.

Statistical Analysis:

Data will be analyzed after de-identification using descriptive statistics or inferential statistics as appropriate and will be collected, organized, and stored through REDcap. T-test will be utilized to compare pharmacist intervention versus usual care on the primary outcome. Descriptive statistics will be utilized to report secondary outcomes.

Feasibility of Project:

The anticipated start date for patient enrollment is November 2024. Statistical analysis will be finalized by April 2025. Anticipate presentations/publication in May or June 2025.

Informed Consent:

Participants will be required to provide signed informed consent prior to inclusion in the study.

References:

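### Clinic mix can differ between the arms: the provider route and active-patient rule name internal medicine only, and controls are a random draw across the clinics with no stratification or adjustment by clinic

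*Combined protocol and SAP*

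**What the plan says.** **Clinics.** Inclusion Criteria require a "PCP at 1 of 6 identified clinics". As the text reads, Practice Sites lists three internal medicine practices, the last being "Ardsley Internal Medicine – Harrisburg", and two family medicine practices: "Atrium Health Primary Care Cabarrus Family Medicine – Locust" and "Atrium Health Primary Care Cabarrus Family Medicine - Midland".

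**Intervention arm.** Under Patient Identification, "Internal medicine providers and PharmDs will identify patients who are not meeting LDL goals for secondary prevention". The same section allows SlicerDicer to be used "potentially for the intervention arm if referrals alone do not meet the sample size goal". Exclusion Criteria remove "Patients who are no longer an active patient of one of the internal medicine practices".

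**Control arm.** Under Control Group, "Patients meeting inclusion criteria will be pulled from SlicerDicer". Patients whose provider has already referred them are taken out, and charts are then chosen at random from the rest. The goal is 75 patients per arm. This section mentions neither the exclusion criteria nor clinic.

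**Analysis.** Statistical Analysis plans a t-test between arms on the primary outcome (LDL below 55, yes or no), with no covariates. Clinic is not a named item in the data list.

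**The concern.** The arms are filled by different mechanisms. One depends on who refers. The other is a random sample of whoever meets the inclusion criteria at the identified clinics. Two lines that bear on clinic are worded for internal medicine, while the site list also covers family medicine. Nothing in the sampling or the analysis brings the two clinic mixes together.

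Clinic may plausibly affect prescribing habits, access to newer agents and how often lipids are tested, although the documents give no data on this. If usual-care goal attainment differs between clinics and the mix differs between arms, part of the observed difference belongs to clinic and not to the pharmacist. If clinic is not recorded, this cannot be examined or corrected afterwards.

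**Working it through.** **1. The plan's own figure.** The only figure is the goal of 75 per arm. It comes without a significance level, power, expected rates or effect size, so it cannot be reproduced. It is used below only as n.

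**2. Count of sites.** 3 internal medicine + 2 family medicine = 5 listed, against 6 in the inclusion criterion. The list has a gap between the two groups, where a line may be missing from the text version. Nothing below depends on the sixth clinic except the illustrative share noted in step 4.

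**3. Routes into each arm for a family medicine patient.**

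| Route | Intervention | Control |
|---|---|---|
| Provider identification | Not named | Not applicable |
| PharmD identification | Open, no specialty limit | Not applicable |
| SlicerDicer | Only as a possible top-up | Open |

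The effect of the active-patient exclusion depends on how it is read:
- *Literal, applied to both arms:* no family medicine patient enters either arm, so there is no family-versus-internal imbalance. But two listed sites can then contribute nobody, which contradicts the inclusion criterion and the site list.
- *Loose wording for all sites, with the identification line equally loose:* no imbalance is written into the rules. Referral and a random draw still need not give the same mix across clinics.
- *Provider route strict, exclusion loose or not applied to controls:* family medicine enters the control arm at its share of the report, but enters the intervention arm only through PharmDs or the top-up.

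**4. Illustrative size.** Let s_C and s_I be the family medicine shares in the control and intervention arms, p the goal attainment in internal medicine, and p - g that in family medicine. With no pharmacist effect, attainment is p - s_I × g in the intervention arm and p - s_C × g in the control arm, so

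bias = (s_C - s_I) × g.

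All inputs are assumptions. s_C = 40% is 2 of 5 clinics if they are equal in size. If there is a sixth clinic that is not family medicine, it is 2/6 = 33%. p is set at 30%. The two-sided 5% rejection rate uses the normal approximation with n = 75 per arm and d the bias: Φ((d - 1.96 × SE0)/SE1) + Φ((-d - 1.96 × SE0)/SE1), where SE0 is the pooled and SE1 the unpooled standard error.

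| s_C | s_I | g (points) | Bias (points) | Rejection rate with no pharmacist effect |
|---|---|---|---|---|
| 40% | 0% | 5 | 2 | 5.8% |
| 40% | 0% | 10 | 4 | 8.4% |
| 40% | 0% | 20 | 8 | 20.0% |
| 40% | 10% | 5 | 1.5 | 5.5% |
| 40% | 10% | 10 | 3 | 6.9% |
| 40% | 10% | 20 | 6 | 13.5% |
| 20% | 0% | 10 | 2 | 5.8% |
| 60% | 0% | 10 | 6 | 13.1% |
| equal shares | equal shares | any | 0 | 5.0% |

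Worked row (40%, 0%, 10 points): bias = (0.40 - 0) × 10 = 4 points; rates 0.30 and 0.26; SE0 = √(2 × 0.28 × 0.72/75) = 0.0733; SE1 = √((0.30 × 0.70 + 0.26 × 0.74)/75) = 0.0732; Φ(-1.416) + Φ(-2.508) = 0.078 + 0.006 = 0.084.

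The sign reverses if family medicine does better.

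**The case against.** The strongest reply is that this is a wording mismatch and that a bias has not been shown. Much of that stands.

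- **Other routes exist.** The identification line names PharmDs without a specialty limit. The visit section describes pharmacists embedded in study clinics, and the text on medication adjustment says pharmacist services already operate at every practice. SlicerDicer may also top up the intervention arm. A reader might infer that family medicine clinics supply few or no intervention patients, but the documents give no referral counts and do not support that.
- **No imbalance is fixed by rule.** A reader might infer that the arms sample different clinic populations by rule. Step 3 shows that this needs a mixed reading: strict for provider referral, but loose for the exclusion or waived for controls. The exclusions form a general list, and nothing exempts controls from it.
- **Six against five.** A reader might take this as an error in the plan. It is only a query to the sponsor, since a line may be missing.
- **The size is assumed throughout.** No passage gives clinic sizes, attainment by clinic, or which type does better. At 30% attainment the standard error of the difference is √(2 × 0.30 × 0.70/75) = 7.5 points, so 3-4 points is about half a standard error.
- **A late control draw has its own hazard.** Controls must have a latest LDL above 55, and no index date is given. A report run late would drop usual-care patients who had already reached goal, which would lower the control rate and favour the intervention. Any delay to the draw must deal with this.

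What the reply does not answer is that the two arms are filled differently, the wording does not match the site list, and neither the draw nor the analysis controls clinic mix.

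**Conclusion.** The point holds as a weakness that is cheap to repair. The identification and active-patient lines do not fit the site list, controls are drawn without regard to clinic, and the primary comparison is unadjusted. Clinic mix can therefore differ between arms, and differences in usual care between clinics could be counted as a pharmacist effect or mask one.

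The size and direction are unknown. The 3-4 points rest on three assumptions: 40% family medicine among controls, 0-10% in the intervention arm, and a 10-point gap in attainment. With equal clinic mix the bias is zero whatever the gap. The documents support neither a proven imbalance nor an error in the site count.

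**What to change.** 1. Reconcile the identification line and the active-patient exclusion with the site list, so that one clinic list applies to both arms. State that the same inclusion and exclusion criteria apply to controls. Ask the sponsor to confirm the sixth clinic.
2. Record clinic for every patient.
3. Draw the controls stratified by clinic, in proportion to the intervention patients from each clinic. A clinic with no intervention patients then supplies no controls. The alternative is to adjust the primary comparison for clinic.
4. Define control eligibility, including the LDL criterion, at a fixed index date at the start of the study period. Freeze that report and sample from it, so that waiting for the clinic counts does not remove controls who later reach goal.

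**Cost.** Wording edits, one extra data field, and a per-clinic draw from a report that must already filter on the PCP's clinic. The final control draw has to wait for the intervention clinic counts, which is workable because control charts are reviewed retrospectively. The change does not remove patient-level selection: intervention patients are chosen mainly by referral, while controls are a random draw of patients not referred.

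### Observation time and LDL testing differ by arm, and controls have no index date, so the primary comparison mixes LDL control with observation

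*Combined protocol and SAP*

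**What the plan says.** **Calendar.** Methods/Data Collection states: "The study period is expected to be 5 months (anticipated November 2024-March 2025"). Feasibility of Project starts enrolment in November 2024 and has the analysis finished by April 2025. No last-enrolment date or minimum follow-up is given.

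**Entry.** Inclusion Criteria require "Most recent LDL value > 55", with no reference date and no look-back limit.

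**Intervention arm.** The initial-visit section includes "Order appropriate lab work". It then says "Follow up visits will be scheduled every 6-8 weeks as needed based on patient-specific needs" and "Once LDL<55 (controlled), no further follow up will be scheduled with PharmD". Follow up visits begin with "Repeat lipid panel prior to appointment, review results". The closing paragraph before Control Group describes the study as "offering additional care services provided by a PharmD for closer follow up".

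**Control arm.** Control Group says "Patients meeting inclusion criteria will be pulled from SlicerDicer", with no date for the pull. Patients already referred to the project are left out, and a random selection is then reviewed retrospectively for the study period. No LDL is scheduled and no per-patient start date is set.

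**Endpoint.** The primary endpoint is LDL below 55, yes or no. It has no time point, no choice among several LDL values, and no rule for a patient with no later LDL. The secondary endpoint, percent LDL reduction, does name a value (the lowest), but only for itself.

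**The concern.** Every patient enters with an LDL above goal. To be recorded as at goal, a patient must have a later LDL, and that depends on how long the patient is observed and whether anyone orders a test. Both differ by arm. One arm has planned panels counted from a personal start date. The other has the full calendar period and whatever usual care orders.

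Some of that difference is the intervention itself, since closer follow-up is what is on offer. But more testing is not the same as lower LDL, and the plan has no means of telling them apart. Patients enrolled late may have no time for a follow-up panel, which works the other way.

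The undated entry criterion adds a separate problem. A control pull made after the period has begun selects on LDL values that may belong to the outcome period. It removes controls whose latest LDL is by then at goal.

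**Working it through.** The plan's target of 75 per arm has no calculation behind it, so there is no planning figure to reproduce. The check uses the calendar, then an illustration.

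**1. Who can reach a follow-up panel**

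Inputs from the protocol: November 2024 to March 2025, and visits every 6-8 weeks. Assumptions: 1 November to 31 March (151 calendar days, both ends counted), uniform enrolment, and a first panel at 6 or 8 weeks.

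- Last initial visit allowing a panel by 31 March: 31 March minus 56 days = 3 February; minus 42 days = 17 February.
- Enrolment to 31 March: 95/151 = 0.63 (8 weeks) or 109/151 = 0.72 (6 weeks) reach a panel. So 28-37%, about 21 to 28 of 75, do not.
- Enrolment to 28 February: 95/120 = 0.79 or 109/120 = 0.91 reach one.
- Enrolment to 31 January: all reach one.

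**2. What unequal testing does when the arms truly do not differ**

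Assumptions, none from the documents: 30% true attainment in both arms regardless of follow-up; every intervention patient who reaches a first visit is tested; 50, 70 or 90% of controls are tested over the period; untested patients count as not at goal.

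Bias = 0.30 × (intervention share tested − control share tested). The bracketed figures are false-positive rates for the pooled t-test, 75 per arm, two-sided 0.05 (level and sidedness assumed), by exact binomial enumeration.

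| Enrolment ends | Controls 50% tested | 70% | 90% |
|---|---|---|---|
| 31 January | +15 points (0.60) | +9 (0.24) | +3 (0.07) |
| 28 February | +9 to +12 (0.28-0.46) | +3 to +6 (0.07-0.14) | -3 to 0 (0.05-0.07) |
| 31 March | +4 to +7 (0.10-0.19) | -2 to +1 (0.05-0.06) | -8 to -5 (0.12-0.22) |

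The extremes are 0.30 × (1.0 − 0.5) = +15 points and 0.30 × (0.63 − 0.9) = -8 points.

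**3. The same model, tested patients only**

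If testing is unrelated to attainment, this analysis is unbiased and loses only precision. If controls at goal are r times as likely to be tested as other controls, observed control attainment is 0.3r/(0.3r + 0.7). At r = 1.5 this is 0.39, a bias of about -9 points. At r = 2/3 it is 0.22, a bias of about +8 points.

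**4. The date of the control pull**

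If controls are selected at period end on a most recent LDL above 55, and the latest LDL is also the endpoint, no control can be at goal. Control attainment is then 0% by construction, whatever the true rate. This needs two choices that the documents do not state: the pull date and the latest-LDL rule.

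**The case against.** The omissions are plain, but five objections limit what follows from them.

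- **The model shows less than the design argument.** Attainment is held at 30% whatever the follow-up, so observation time acts only through whether a panel exists. In that model a tested-only analysis over the existing period is already unbiased. This stands: apart from the pull date, the figures quantify unequal testing and not longer exposure. The case for index dates rests on the design.
- **A short fixed window can cost more than it gains.** For 50% v 20% at goal with enrolment to 31 March, tested-only power over the existing period is about 83/89/93% (47 intervention patients v 37/52/67 controls). With days 29-84 closing by 31 March it is about 54/70/81% (33 v 17/27/43). This stands, so such a window is an option and not a requirement.
- **Direction.** A reader might infer that the plan favours the intervention. The documents do not support that: late enrolment with well-tested controls reverses the sign. Follow-up is also only as needed, so full testing of intervention patients is an upper bound. On the other side, labs ordered at the initial visit might supply an LDL to some patients with no follow-up panel.
- **Zero control attainment.** A reader might infer that controls cannot succeed. That is a worst case. The only LDL-selection rule in the text is the lowest value, for a secondary endpoint, and the visit section treats an LDL below 55 as controlled. Any LDL below 55 during the period is a plausible reading of the endpoint, and under it 0% is not automatic.
- **Controls do have an observation period.** They are reviewed over the study period. What is missing is a per-patient start date aligned with the intervention arm.

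**Conclusion.** The concern holds as a design weakness that should be corrected. Followed as written, the plan gives the arms different observation time and different LDL testing, selects controls on an undated criterion, and does not say which LDL decides the endpoint. A difference in the primary endpoint could not be attributed to LDL control alone.

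Confidence is high for these omissions and for the unequal ascertainment, which rest on the text. It is low for magnitude. The range of about -8 to +15 points rests on assumed attainment, testing rates and enrolment pattern, and on counting untested patients as failures. The 28-37% without a scheduled follow-up panel rests on uniform enrolment to 31 March. What needs no assumed rate is that any control pull after the period starts removes controls whose latest LDL has by then reached goal.

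**What to change.** Settle the following before outcome data are pulled.

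1. **Index date and entry.** Use the initial visit in the intervention arm. Give each control a date sampled from the intervention initial-visit dates, at the same clinic where possible. In both arms apply LDL >55 to the last LDL on or before index, within a stated look-back limit. Do not select controls on any LDL after index.
2. **Endpoint.** Count it over the same post-index follow-up in both arms, with one LDL-selection rule for both. The length and the rule are the sponsor's choice. Running from index to 31 March in both arms would balance observation time without dropping anyone, though late entrants would still have little follow-up. A fixed window, for example days 29-84 with the first LDL in it, is another option. It would keep only index dates up to 6 January, about 75 × 67/151 = 33 intervention patients if enrolment is uniform to 31 March. Otherwise it would extend the chart look-up to 23 June 2025, past the planned April analysis. It also ignores later titration.
3. **Untested patients.** Report the proportion with a post-index LDL by arm. Show the result among tested patients and also with untested counted as not at goal, and name in advance which is primary. State that the tested-only result assumes testing is unrelated to attainment and that the other favours the more-tested arm.

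The cost is protocol and SAP wording, date assignment during chart review, and possibly some precision.

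### The primary t-test ignores treating pharmacist and clinic, so its standard error may be wrong; record both, adjust for clinic, and add a sensitivity analysis for pharmacist clustering

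*Combined protocol and SAP*

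**What the plan says.** The Statistical Analysis section says: "T-test will be utilized to compare pharmacist intervention versus usual care on the primary outcome". The only other wording on inference is that data are analysed "using descriptive statistics or inferential statistics as appropriate", after de-identification. There is no term for pharmacist, provider or clinic, no clustered standard error and no ICC. The primary endpoint is binary (LDL below 55, yes or no).

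On size, the Control Group section says: "The goal will be to include 75 patients in both the intervention and control arms". No derivation is given.

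On delivery, the initial-visit section says: "Each pharmacist working on this project either practice as a CPP or are under the direct supervision of CPP". Under Follow up visits, an initial or follow-up visit "may be completed by another embedded pharmacist within one of the clinics included in study due to schedule availability", and "Members of the PharmD team will be trained and follow the protocol during their visits". Neither the number of pharmacists nor their caseloads are stated.

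On how patients enter, Patient Identification says: "Internal medicine providers and PharmDs will identify patients who are not meeting LDL goals". A SlicerDicer search may top up the intervention arm if referrals fall short. Controls are a random selection from a SlicerDicer report under the same inclusion criteria, which require a PCP at one of six clinics. Nothing matches or stratifies the two arms by clinic.

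The data-collection list names neither clinic nor treating pharmacist.

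**The concern.** A two-sample t-test takes its standard error from the spread of individual patients and assumes that they are independent. Two features of this design put that assumption in doubt.

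- **Pharmacist, in one arm.** Study pharmacists adjust treatment, assess adherence and deal with access, all of which bear on reaching LDL below 55. Patients who share a pharmacist may therefore have correlated outcomes. Controls have no study visits, so this clustering sits mainly in the intervention arm.
- **Clinic, in both arms.** Referral and random draw can produce different clinic mixes. If goal attainment differs between clinics, part of the arm difference is then a clinic difference.

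The stated objective concerns pharmacist intervention against usual care. If a few pharmacists carry the arm, one unusually effective or ineffective pharmacist could move the result, and the interval would not show it. If clinic and pharmacist are not captured before the data are de-identified, the question may not be answerable later.

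**Working it through.** **Inputs from the documents:** 75 per arm, t-test, binary endpoint, more than one pharmacist, six clinics by the inclusion criteria. **Not in the documents, so assumed:** two-sided 5% level, number of pharmacists k, equal caseloads, ICC, and a 20% event rate for the simulations. The figure of 75 per arm cannot be reproduced, because no alpha, power or event rates are given.

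**1. Pharmacist clustering in the intervention arm only**

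- Caseload: m = 75/k
- Design effect in that arm: DE = 1 + (m − 1) × ICC
- True SE of the difference ÷ t-test SE: r = √((DE + 1)/2), with equal variances in the two arms
- Actual type I error: 2 × (1 − Φ(1.96/r))

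Example, k = 5 and ICC 0.05: m = 15; DE = 1 + 14 × 0.05 = 1.70; r = √(2.70/2) = 1.162; 1.96/1.162 = 1.687; type I error 9.2%. Effective intervention n = 75/1.70 = 44.1.

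| k (m) | ICC | DE | Effective n | r | Type I error |
|---|---|---|---|---|---|
| 5 (15.0) | 0.02 | 1.28 | 58.6 | 1.07 | 6.6% |
| 5 | 0.05 | 1.70 | 44.1 | 1.16 | 9.2% |
| 5 | 0.10 | 2.40 | 31.2 | 1.30 | 13.3% |
| 7 (10.7) | 0.02 | 1.19 | 62.8 | 1.05 | 6.1% |
| 7 | 0.05 | 1.49 | 50.5 | 1.12 | 7.9% |
| 7 | 0.10 | 1.97 | 38.0 | 1.22 | 10.8% |

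Over a wider range, k = 3 to 10 and ICC 0.01 to 0.10, type I error runs from 5.4% (k = 10, ICC 0.01) to 18.6% (k = 3, ICC 0.10). A beta-binomial simulation (40,000 trials per setting, pooled t-test) agrees with the formula. For k = 5 it gives 5.7%, 6.5%, 9.5% and 13.4% at ICC 0.01, 0.02, 0.05 and 0.10.

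**2. Clinic effects shared by both arms** (same simulation, five clinics)

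| Clinic mix | ICC 0.01 | 0.02 | 0.05 | 0.10 |
|---|---|---|---|---|
| Balanced, 15 per clinic in each arm | 5.1% | 4.8% | 4.6% | 3.9% |
| Unbalanced, 30/20/12/8/5 against 15 each | 5.1% | 5.3% | 6.2% | 7.0% |

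The direction depends on the mix. With a balanced mix the unadjusted t-test is about right or slightly conservative; with an unbalanced mix it rejects too often. Adding clinic as a fixed effect brought type I error back to about 5% in both cases.

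**3. Price of a primary model with random pharmacist effects**

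With k = 5, Satterthwaite degrees of freedom are (DE + 1)² ÷ (DE²/4 + 1/74). That is about 12, 10 and 8 at ICC 0.02, 0.05 and 0.10. The interval is then 1.17, 1.31 and 1.52 times as wide as the t-test interval.

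**The case against.** The strongest reply is that the documents do not show that clustering exists or how large it is.

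- **A reader might infer that a handful of pharmacists treat the arm and that a subset of providers refers it, so that the p-value is wrong and too small.** The text gives no number of treating pharmacists or referrers. PharmDs also identify patients, and SlicerDicer may supply some. Any calculation for concentrated referral needs invented numbers, and its direction reverses if referrals are spread evenly. This part cannot be asserted.
- **Nesting is not strict.** A patient may see two pharmacists, and the team shares training and a protocol. Both may lower the ICC; neither makes it zero.
- **Controls may also see pharmacists.** The protocol says that PharmD services already exist at each practice. Effects common to both arms partly cancel, so clustering in one arm only is an approximation.
- **The type I figures depend on the null.** They describe pharmacists whose effects vary around an average of zero. If pharmacist care changed nothing for any patient, it would induce no correlation. No passage says that inference is meant to extend beyond these pharmacists, although the objective is worded generally.
- **Referral selection is mainly a bias problem.** That is right, and a clustered standard error would not correct it.

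These points rule out a claim that the standard error is certainly too small, and they weaken the case for making a random-pharmacist model primary. They do not justify leaving clinic and pharmacist unrecorded.

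**Conclusion.** The concern holds in a limited form. The plan's only inferential test assumes 150 independent patients and takes no account of pharmacist or clinic. Its standard error may be too small (pharmacist clustering, unbalanced clinic mix) or slightly too large (shared clinic effects, balanced mix).

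If 5 to 7 pharmacists share the arm equally, a nominal 5% test has a true level of about 6.1-6.6% at ICC 0.02, a modest departure, and 10.8-13.3% at ICC 0.10, which is material. Which of these applies cannot be settled from the documents.

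The stronger step, a primary analysis with random pharmacist effects, is not compelled. With about five pharmacists it leaves roughly 8 to 12 degrees of freedom and a poorly estimated ICC, and statisticians would differ on it. Clinic adjustment is nearly free and is worthwhile whichever way the mix falls. It does not remove pharmacist variation within the intervention arm, so a separate sensitivity analysis is needed. Non-random selection into the intervention arm remains the larger threat to this comparison.

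**What to change.** 1. **Record** a coded clinic for every patient in both arms and, in the intervention arm, a coded initial-visit pharmacist and any covering pharmacist. Do this in REDCap before de-identification. State the number of pharmacists taking part.
2. **Primary analysis.** Replace the t-test sentence with, for example: The arm difference in the proportion with LDL below 55 will be estimated as a risk difference with a 95% confidence interval, adjusted for clinic as a fixed effect.
3. **Pre-specified sensitivity analysis.** Fit a partially nested model with a pharmacist effect in the intervention arm only and small-sample degrees of freedom. Alternatively, multiply the standard error by √((DE + 1)/2) over a stated ICC range such as 0.01 to 0.10, using the observed caseloads. Say in advance that patients are assigned to the initial-visit pharmacist.
4. **Descriptive check.** Report goal attainment by pharmacist, de-identified.

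The cost is up to three data fields and a few sentences of analysis text. Six clinics use five degrees of freedom of the 148 in the t-test. The sensitivity interval will be somewhat wider and the ICC imprecise. None of this corrects referral selection bias, which needs its own remedy.
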